3.1 SAMPLE SIZE CONSIDERATIONS

Assuming a standard deviation (SD) of [REDACTED] and based on an average difference in total SKAMP scores between Placebo and d-ATS of [REDACTED], 74 subjects would need to complete the study to detect a true difference of [REDACTED] in mean total SKAMP scores between placebo and d-ATS at 80% power when testing at a significance level of $\alpha = 0.05$ (2-sided). Assuming a dropout rate of 20%, 90 subjects will be randomized and it is expected that 74 subjects will complete the study. A subject will be considered to have completed the study if the subject received both treatments during the double-blind Treatment Period and have completed both 12-hour classroom sessions during the double-blind Treatment Period.

3.2 RANDOMIZATION

Randomization will occur prior to the start of the double-blind study period. Subjects will be randomized to one of the two treatment sequences (d-ATS then Placebo or Placebo then d-ATS) in a 1:1 ratio. Each eligible subject will be randomized to group assignment by a centralized Interactive Voice Response System (IVRS) /Interactive Web Response System (IWRS). Randomization will be applied centrally, without any stratification factors, across all sites to ensure even distribution of subjects across each treatment sequence.

4. STUDY VARIABLES AND COVARIATES

4.1 PRIMARY VARIABLE

The primary efficacy measure is the mean SKAMP total score. The SKAMP scale is a validated rating scale that assesses manifestations of ADHD in a classroom setting through several subscales, including deportment (behavior) and attention. Multiple SKAMP assessments will be completed at the end of individual classroom sessions across the day by observers who rated each subject on 13 items, using a 7-point impairment scale (0=normal, 6=maximal impairment).

4.2 SECONDARY VARIABLES

4.2.1 SKAMP

The SKAMP total score at each assessment time point will also be used to assess the secondary measures of onset and duration of efficacy.

4.2.2 PERMP

The PERMP, a 5-page math test consisting of 80 problems per page (total of 400 problems), will be used in this study to evaluate effortful performance in the classroom as a measure of efficacy. Subjects will be instructed to work at their seats and to complete as many problems as possible in 10 minutes. The appropriate level of difficulty for each student will be determined based on results of a math pretest administered at screening. Performance will be evaluated using two scores: PERMP-A (number of problems attempted) and PERMP-C (number of problems correct). In order to prevent the subjects from taking the same test more than once during the study, subjects will receive randomized problems in a different version of the test at each assessment.

4.2.3 ADHD-RS-IV

The ADHD-RS-IV is a clinician-rated scale that reflects current symptoms of ADHD based on Diagnostic and Statistical Manual of Mental Disorder, Fourth Edition, Text Revision (DSM-IV-TR) criteria; it is a global assessment that measures the severity of symptoms from visit to visit, but is not utilized to assess symptoms of ADHD over the course of the day. The ADHD-RS-IV consists of 18 items that are grouped into 2 subscales (hyperactivity/impulsivity and inattention). Each item is scored on a 4-point scale from 0 (no symptoms) to 3 (severe symptoms), yielding a total score of 0 to 54.

ADHD-RS-IV Hyperactivity-Impulsivity Subscale includes the following question scores:

- [REDACTED]

ADHD-RS-IV Inattention Subscale includes the scores for the following questions:

- [REDACTED]
- [REDACTED]
- [REDACTED]
- [REDACTED]
- [REDACTED]

- [REDACTED]
- [REDACTED]
- [REDACTED]
- [REDACTED].

4.2.4 CPRS-R:S

The CPRS-R:S is a standard instrument for the assessment of ADHD in children and adolescents. It evaluates problem behaviors as reported by the parent or alternative caregivers. The CPRS-R:S contains 27 items and covers a subset of the subscales and items on the long parent form. Scales include: oppositional, cognitive problems/inattention, hyperactivity, and ADHD index.

4.2.5 CGI

The CGI provides a global evaluation of baseline severity and improvement over time, and, like the ADHD-RS-IV scale, measures global impressions of severity from visit to visit but not over the course of the day. At baseline, the investigator will use the CGI-Severity (CGI-S) to rate severity on a scale that ranges from 1 (normal, not at all ill) to 7 (among the most extremely ill subjects) plus a not assessed option. At each visit thereafter, the clinician will use the CGI-I to rate improvement relative to baseline on a scale ranging from 1 (very much improved) to 7 (very much worse) plus a not assessed option. For analysis, CGI-I and CGI-S scores will be dichotomized.

For CGI-S:

The **non-severe** illness is defined as subjects achieving a score of

- 1: Normal, not at all ill or
- 2: Borderline mentally ill or
- 3: Mildly ill.

The **severe** illness is defined as subjects achieving a score of

- 4: Moderately ill or
- 5: Markedly ill or
- 6: Severely ill
- 7: Among the most extremely ill patients.

Subjects achieving a score of 0: Not assessed will be considered as missing data. The number and percentage of subjects with severe illness and non-severe illness at each time point will be summarized.

For CGI-I

The **responders** are defined as subjects achieving a score of

- 1: Very much improved or
- 2: Much improved or
- 3: Minimally improved on the clinician-rated CGI global improvement item.

The **non-responders** are defined as subjects achieving a score of

- 4: No change or
- 5: Minimally worse or

- 6: Much worse or
- 7: Very much worse.

Subjects achieving a score of 0: Not assessed will be considered as missing data. The number and percentage of responder and non-responders at each time point will be summarized.

The actual values of each question of CGI-S, and CGI-I, severity (severe or non-severe), and responder (yes/no) will be listed.

4.2.6 Safety

Safety will be assessed by evaluating:

- Adverse events (AEs)
- Suicidality [assessed using Columbia Suicide Severity Rating Scale (C-SSRS)]
- Concomitant medications
- Clinical laboratory tests
- Vital signs
- Physical examinations
- Electrocardiograms (ECGs)

4.3 PREDETERMINED COVARIATES AND PROGNOSTIC FACTORS

Demographic and baseline characteristics known to be related to treatment response may be considered for inclusion as covariates in exploratory statistical analysis models.

The effect of the following factors on the primary efficacy analysis (FAS population) will be considered:

- Investigator site
- Optimized dose
- Gender
- ADHD type (inattentive, hyperactive/impulsive, combined, not otherwise specified)
- Baseline ADHD severity (defined as the pre-dose ADHD-RS-IV rating scale at baseline, Visit 0)
- Age group

To ensure summaries from the subgroups are informative, these will only be performed where subgroups include 5 or more subjects in each. Where subgroups have less than 5 subjects the small group will be combined with the next group, if there is a consecutive order to the groupings or with the next smallest group if there is no order.

5. DEFINITIONS

SKAMP Total Score

The SKAMP total score will be the sum of the 13 individual item scores at each timepoint. Missing data will not be handled at an item level, if any of the 13 items are missing for a timepoint then the SKAMP total score will be missing for that timepoint.

Mean SKAMP Total Score

The mean SKAMP total score will be the average of all SKAMP total scores collected over the course of a laboratory assessment day, with the exception of the score from the session prior to dosing.

Onset of efficacy

The onset of efficacy, based on the SKAMP total scores, will be defined as the time of the first assessment time showing statistical significance between d-ATS and placebo. If no significant difference is found at any time point for the onset of efficacy, no onset of efficacy will be deemed to have occurred, and the onset of efficacy will be defined as 'none'.

Duration of efficacy

The duration of efficacy, based on the SKAMP total scores, will be defined as the difference between the time point that indicates that the effect has ended and the onset of efficacy, as defined above. The time point that indicates that the effect has ended will be defined as the first time point at which there is a non-significant difference between the two treatment groups after a time point in which there is a significant difference between the two treatment groups. If there is no time point at which there is a non-significant difference between the two treatment groups after a time point in which there is a significant difference between the two treatment groups, then the end of effect will be defined as 12 hours post-dose.

Onset of effect (50% reduction in SKAMP total score)

Onset of effect of 50% reduction in SKAMP total score is defined for each subject as the first time point at which there is a 50% reduction in SKAMP total score from the pre-dose observation on the same classroom day.

Duration of effect (50% reduction in SKAMP total score)

Duration of effect of 50% reduction in SKAMP total score will be determined by persistence of the 50% reduction from the pre-dose observation in SKAMP total score level. The end of effect will be determined as the first timepoint after onset of effect at which 50% reduction from the pre-dose observation in SKAMP total score is not observed. The duration of effect will be calculated as the difference between the end of effect and onset of effect, in hours.

Age

Age will be calculated as (date of informed consent – date of birth + 1) / 365.25.

Baseline

Baseline is defined as data collected at Visit 0 (Day 0). If data was not collected at Visit 0, the last data available prior to Visit 0 will be used as the baseline data. However during the double

blind crossover phase change from baseline analyses will be performed taking the pre-dose data at the same classroom visit to be the baseline.

Body Mass Index

Body Mass Index (BMI) will be calculated as weight in kg / (screening height in m)².

Prior and Concomitant Medications

Prior medications are defined as those taken prior to the date of first dose of study medication. Concomitant medications are defined as those on or after the date of first dose of study medication through and including the day of the safety follow-up visit. Medications with a missing or incomplete start date will be assumed to be concomitant.

Concomitant medications will be assigned to either the Dose-Optimization Period or the double-blind Treatment Period of the study according to the start date, and will be summarized separately. Concomitant medications for which a missing or incomplete start date makes it impossible to determine which period of the study they started in will be counted as starting in the Dose-Optimization Period.

Treatment-emergent adverse event

A treatment-emergent adverse event (TEAE) is one which first occurs or worsens in severity after the first patch application and not later than 30 days following last patch removal. Adverse events are collected through the last study visit. Those AEs with a start date equal to the date of first patch application will be considered as TEAEs.

Adverse events for which a missing or incomplete start date makes it impossible to determine whether or not they were treatment-emergent will be counted as being treatment-emergent.

Adverse events will be assigned to either the Dose-Optimization Period or the double-blind Treatment Period of the study according to the start date, and will be summarized separately. Adverse events for which a missing or incomplete start date makes it impossible to determine which period of the study it started in will be counted as starting in the Dose-Optimization Period

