<treatment*timepoint> 0 0 0 0 0 0 0 0 0 -1 0 0 0 0 0 0 0 0 0 0 1  
/ cl;
```

The two treatment levels will be: d-ATS (5, 10, 15, 20 mg doses combined) and placebo. Continuous summary statistics will be presented for the SKAMP total score at each time point for Visits 6 and 7 for the FAS population. Raw means, LS means, differences in LS means, and 95% CI for the difference between treatment arms, and p-values will be calculated for each post-dose time point and for mean score over the treatment day for the FAS population.

The SKAMP total scores will also be plotted by time point for the FAS population.

Scaled residual and random effects plots will be considered to check the assumptions behind the mixed model.

The assessment of treatment differences will follow the closed testing procedure described in Section 7. The closed testing procedure starts from the time-point of 1 hour post-morning dose, then 2, 3, 4.5, 6, 7, 9, 10 and 12 hours post-dose. At each timepoint the order of testing will be onset of efficacy followed by duration of efficacy, before moving to the next timepoint. Duration of efficacy will not be considered until onset of efficacy has been determined.

- The onset time of efficacy action will be determined as the first post-dose time where the difference between the two treatments is statistically significant (i.e., $p \leq 0.05$).
- If the difference between the two treatments is statistically significant (i.e., $p \leq 0.05$) at the 1 hours post-dose time point, the duration of efficacy will be claimed as the difference in hours between the end of efficacy; the last consecutive time point at which the difference is still statistically significant (i.e., $p \leq 0.05$) and onset of efficacy. If there is no time point at which there is a non-significant difference between the two treatment groups after a time point in which there is a significant difference between the two treatment groups, then the end of efficacy will be defined as 12 hours post-dose.

For example, if a statistically significant difference in mean SKAMP total scores for d-ATS vs. placebo was determined at 1 hour post-dose and statistical significance was measured at all time-points up to and including 10 hours post-dose, but statistical significance was not reached at 12 hours post-dose, onset of clinical efficacy and end of clinical efficacy would be defined as 1 hours post-dose and 10 hours post-dose, respectively, with duration of efficacy being 9 hours.

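### SAP 5 and SAP 7.1.3.1 both read one non-significant classroom session as the end of efficacy, and they give different durations (11 h and 9 h) on the SAP's own example

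*SAP*

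**What the plan says.** SAP 5 (Definitions, Duration of efficacy) subtracts the onset time from the time of ending. The time at which the "effect has ended will be defined as the first time point at which there is a non-significant difference" between treatments, after a session that was significant. If no such session occurs, the end is set to 12 hours.

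SAP 7.1.3.1 places the end at the last consecutive session that is still significant at p ≤ 0.05. Its worked example has significance from 1 h through 10 h and none at 12 h: "onset of clinical efficacy and end of clinical efficacy would be defined as 1 hours post-dose and 10 hours post-dose" respectively, with a duration of 9 hours.

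SAP 7 tests the post-dose times in order and stops at the first failure. SAP 7.1.3.1 also plans least-squares mean differences with 95% confidence intervals at each post-dose time. It then repeats the primary analysis without the sessions before onset and after the last one in the duration window.

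SAP 3.1 gives power only for the day-level measure: "74 subjects would need to complete the study to detect a true difference of" a redacted amount "in mean total SKAMP scores between placebo and d-ATS at 80% power", two-sided alpha 0.05. SAP 5 defines that measure as the average over the day without the pre-dose session.

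**The concern.** Stopping formal tests at the first failure is correct error control. It does not show that the drug has stopped working. A non-significant session can mean no effect, a smaller effect, or the full effect missed by chance, and neither definition separates these. No power is stated for a single session, and a long duration needs an unbroken run of significant sessions.

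The trial could therefore report that efficacy ended at an hour fixed by noise. That hour also sets which sessions the follow-on sensitivity analysis of the primary variable drops. Because the two sections define the end differently, the reported duration also depends on which one the programmer follows.

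**Working it through.** **1. The two definitions on the SAP's own example** (significant at 1 to 10 h, not at 12 h).

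- SAP 5: the first non-significant time is 12 h, so duration = 12 − 1 = 11 h.
- SAP 7.1.3.1: the last consecutive significant time is 10 h, so duration = 10 − 1 = 9 h.
- SAP 5 if significance had held at 12 h as well: the end is set to 12 h, so duration = 12 − 1 = 11 h.

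SAP 5 thus gives the same 11 h whether the 12 h session succeeds or fails. No assumption is needed for this step.

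**2. Inputs for power.** From SAP 3.1: 74 completers, 80% power, two-sided 0.05. From SAP 5 and 7.1.1: nine post-dose sessions in the day mean (1, 2, 3, 4.5, 6, 7, 9, 10 and 12 h). The SD and the difference are redacted in the public copy, so the figure of 74 cannot be reproduced. The design can be inverted instead:

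1.960 + 0.842 = 2.802, and 2.802 / √74 = 0.326 SD of the paired day-mean difference (0.330 with the t distribution).

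**3. From the day mean to one session.** Assume a constant effect over the nine sessions, equal session variances, and a common correlation r between the sessions' d-ATS minus placebo differences. The documents do not give r. The variance of the day mean is (1 + 8r)/9 of a session's variance, so

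miss rate = 1 − Φ(2.802 × √((1 + 8r)/9) − 1.960).

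At r = 0.5: √(5/9) = 0.745; 2.802 × 0.745 = 2.088; 1 − Φ(0.128) = 45%.

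At r = 1 the miss rate is 20%, the floor. At r = 0 it is 85%. If the redacted SD refers to a single session, it is 20%.

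**4. The run of sessions.** I simulated nine correlated z-statistics (200,000 trials per r) with an effect that never ends. Onset was the first significant session. Trials were counted if the day mean was significant and an onset existed.

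| Assumed r | One session misses | All nine significant (all trials) | An end declared by 12 h | Same, sessions to 9 h only |
|---|---|---|---|---|
| 0.3 | 59% | 2% | 95% | 88% |
| 0.5 | 45% | 13% | 81% | 74% |
| 0.7 | 33% | 34% | 55% | 50% |
| 0.9 | 24% | 60% | 24% | 21% |

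**5. Larger true effect.** The noncentrality in step 3 is multiplied by 1.5 or 2.

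| Assumed r | Miss, 1.5× | End declared, 1.5× | Miss, 2× | End declared, 2× |
|---|---|---|---|---|
| 0.3 | 27% | 76% | 7% | 34% |
| 0.5 | 12% | 41% | 1% | 7% |
| 0.7 | 5% | 16% | 0.2% | 1% |
| 0.9 | 2% | 4% | <0.1% | 0.1% |

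**The case against.** The strongest reply is that the percentages are not properties of this trial. They rest on an assumed correlation, a redacted design effect and a constant effect through 12 h. Patches come off at 9 h, so the 10 h and 12 h sessions may show real fading. The calculation also uses paired tests, whereas the example code in SAP 7.1.1 has independent residuals and no subject effect. All of this stands. A reader might infer that reported ends would reflect low power rather than loss of effect, or that the miss rate is a known figure. The documents support neither: the rule cannot tell the two causes apart, and only the 20% floor holds across r. The coded model does not rescue the rule. Under assumed correlations of 0.6 to 0.8 within a day and 0.4 to 0.6 across days, it missed about 70% to 84% of the time, against 39% to 57% with a paired standard error.

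A reader might also infer that duration is always biased short. That is not established. SAP 5 runs to the first failed session, past the last one at which superiority was shown, and so can overstate the demonstrated duration.

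Third, SAP 7.1.3.1 already uses the last consecutive significant session, and the per-session intervals are planned. True, so under that section the hour itself would not change. But no rule uses the intervals to define the end, the label still asserts an end of clinical efficacy, and SAP 5 still says something else. The planned Kaplan-Meier analysis of a 50% SKAMP reduction is informative but answers a different, within-subject question.

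Finally, significant sessions after the first failure could not be claimed as formal findings. That is right; they would be nominal only.

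**Conclusion.** The point holds in two parts. The contradiction between SAP 5 and SAP 7.1.3.1 (11 h against 9 h) follows from the text alone. The reading of non-significance as an end of effect also stands in both sections. With a constant effect and equal session variances, a single session misses the design effect at least 20% of the time, and 24% to 59% of the time for an assumed r of 0.9 to 0.3. A reported end may therefore reflect limited power.

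How often that would happen is uncertain. At the design effect, a false end follows a significant primary result in 24% to 95% of trials over that range of r. At twice the design effect it does so in 7% or less for r of 0.5 and above. The SAP should be changed. The primary analysis is not affected; duration and the sensitivity analysis built on it are.

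**What to change.** Use one definition in SAP 5 and SAP 7.1.3.1: *the last consecutive post-dose time at which superiority over placebo was demonstrated*. Report duration as *demonstrated from onset through X hours*. Remove the statements in both sections that the effect or clinical efficacy ended. Keep the ordered stop at the first failure. Show the planned differences and 95% confidence intervals for every session beside the result, and mark p-values after the first failure as nominal. Use the same definition for the sessions kept in the follow-on sensitivity analysis.

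No margin for declaring absence of effect is needed. One set at half the design difference would confirm a truly absent effect with probability Φ(½ × session noncentrality − 1.960), which is only 14% (r = 0.3) to 27% (r = 0.9).

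The cost is SAP wording before database lock, with no new data or tests. The downside is that the report gives no definite end time.

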Duration of effect for 50% reduction in SKAMP total score will be determined by persistence of the reduction of 50% from the pre-dose observation in SKAMP total score. The end of effect will be determined as the first timepoint after onset of effect at which the 50% reduction in SKAMP total score is not observed. The duration of effect will be calculated as the difference between the end of effect and onset of effect, in hours. Duration of effect will be analyzed using the same methodology as the onset of effect. Subjects that record a 50% reduction in the SKAMP total score from the baseline value such that duration of effect continues at their final assessment time for that classroom day will be censored at that time. Subjects without an onset of effect will be excluded from the analysis of duration of effect. A sensitivity analysis will be performed where subjects without an onset of effect will be imputed to have duration of effect of 0 hours.

Supportive analysis of onset of efficacy and duration of efficacy will be conducted using the same approach for the Completers population.

Once onset and duration of efficacy are estimated (using the MMRM approach analysis for the FAS, as described above), the sensitivity analysis will be conducted for primary variable as specified in section 7.1.1 by excluding data from time points before onset and after the last time point included into the duration of efficacy.

All data, including derived values, will be listed.

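### The SAP ends the duration of efficacy by two different rules, so its own worked example gives 9 hours in Section 7.1.3.1 and 11 hours under Section 5.

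*SAP*

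**What the plan says.** SAP Section 5 defines duration of efficacy as the "difference between the time point that indicates that the effect has ended and the onset of efficacy". The end point in that subtraction "will be defined as the first time point at which there is a non-significant difference between the two treatment groups", provided an earlier time was significant. If significance is never lost, "then the end of effect will be defined as 12 hours post-dose".

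SAP Section 7.1.3.1 describes the same quantity, from the same mixed model. There the end of efficacy is "the last consecutive time point at which the difference is still statistically significant", and duration is that time minus onset. The rule is introduced for the case where the 1-hour difference is significant. Its fallback matches Section 5: "then the end of efficacy will be defined as 12 hours post-dose". The section then works an example with significance at every time from 1 to 10 hours and none at 12 hours. Onset is 1 hour and end is 10 hours, "with duration of efficacy being 9 hours".

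Later in Section 7.1.3.1, the paragraph introducing the mixed-model and survival approaches refers back to Section 5 for the definitions. The section also plans a sensitivity analysis of the primary variable "by excluding data from time points before onset and after the last time point included into the duration of efficacy".

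Protocol Section 8.2.2 defines onset but gives no rule for when efficacy ends. SAP Section 1.1 declares no changes from the protocol.

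**The concern.** One rule stops at the last time a difference was shown. The other runs on to the first time a difference was not shown. These are different times unless significance persists to the final assessment, so one set of results can yield two reported durations, each defensible from the SAP text. Unless this is settled before unblinding, the choice could be made with the results in view.

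Section 5 has a further weakness. It sets the end at 12 hours both when the 12-hour test fails and when significance is never lost. A product whose effect is not shown at 12 hours then reports the same duration as one whose effect is. With patches removed at 9 hours (Protocol Section 5.3.5), the 10- and 12-hour tests are the ones that speak to persistence after removal, and Section 5 blurs the last of them.

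The sensitivity analysis of the primary variable uses the same window to decide which times to drop, so the ambiguity may carry into it.

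**Working it through.** **Inputs.** Post-dose test times from SAP Section 7.1.3.1: 1 hour, "then 2, 3, 4.5, 6, 7, 9, 10 and 12 hours post-dose". The gaps between successive times are 1, 1, 1.5, 1.5, 1, 2, 1 and 2 hours.

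**Formulas.**
- Section 7.1.3.1: duration = last consecutive significant time - onset.
- Section 5: duration = first non-significant time after onset - onset, with 12 hours as the end if there is none.

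**Step 1: reproduce the SAP's figure.** Onset is 1 hour and the last consecutive significant time is 10 hours. Section 7.1.3.1 gives 10 - 1 = 9 hours, as printed.

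**Step 2: apply Section 5 to the same pattern.** The first non-significant time is 12 hours, so duration = 12 - 1 = 11 hours. The excess is 11 - 9 = 2 hours, and 2/9 = 22%. The SAP does not print the 11; it follows directly from the Section 5 rule.

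**Step 3: significance never lost.** Both rules set the end at 12 hours and give 12 - 1 = 11 hours. Section 5 therefore returns 11 hours here and in Step 2, while Section 7.1.3.1 separates the two cases (11 against 9).

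**Step 4: every end point of an unbroken run with onset at 1 hour.**

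| Last significant time (h) | First non-significant time (h) | Duration, 7.1.3.1 (h) | Duration, Section 5 (h) | Difference (h) |
|---|---|---|---|---|
| 1 | 2 | 0 | 1 | 1 |
| 2 | 3 | 1 | 2 | 1 |
| 3 | 4.5 | 2 | 3.5 | 1.5 |
| 4.5 | 6 | 3.5 | 5 | 1.5 |
| 6 | 7 | 5 | 6 | 1 |
| 7 | 9 | 6 | 8 | 2 |
| 9 | 10 | 8 | 9 | 1 |
| 10 | 12 | 9 | 11 | 2 |
| 12 | none | 11 | 11 | 0 |

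The rules agree in one of the nine rows. Elsewhere the difference is the gap to the next assessment.

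**The case against.** The best defence of Section 5 is that efficacy is tested only at fixed times. If 10 hours is significant and 12 hours is not, the change lies somewhere between them. Section 7.1.3.1 reports the lower end of that interval and Section 5 the upper end. Section 5 calls its time the one that signals the effect has ended, so it does not claim an effect there. The SAP uses the same first-time-lost convention for the separate per-subject duration based on a 50% reduction. All of this is fair: Section 5 could stand as a convention on its own. It cannot stand beside Section 7.1.3.1, and it still cannot tell failure from success at 12 hours.

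Three smaller points also stand.
- The Section 7.1.3.1 rule is worded only for significance at 1 hour, and it gives a duration of zero if the onset time is the only significant one.
- The effect on the sensitivity analysis is uncertain. That text points to the mixed-model estimates described above it, and a time at which the effect has ended can be read as outside the window, so both rules might keep the same data.
- The cross-reference to Section 5 mixes the terms effect and efficacy.

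It can also be said that the worked example shows what was intended and that results at each time are reported anyway. That limits the harm, but it does not remove the contradictory definition.

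**Conclusion.** The SAP contradicts itself on a secondary endpoint, and no other text in the SAP or protocol resolves it. The reported duration differs by 1, 1.5 or 2 hours whenever significance is lost at or before 12 hours, and by nothing when it holds from onset through 12 hours. In the SAP's own example the difference is 2 hours (11 against 9). These sizes assume the planned assessment times and, for the table, onset at 1 hour with an unbroken run of significance.

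No test decision, treatment estimate or primary conclusion changes. The matter should be corrected, but it does not threaten the main result. The per-subject duration based on a 50% reduction is worded consistently and is not affected.

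**What to change.** Replace the Section 5 paragraph with the rule that Section 7.1.3.1 applies in its example. End of efficacy is the last time in the unbroken run of significant differences that starts at onset, and duration is that time minus onset. Use 12 hours as the end only if the 12-hour difference is itself significant. Put the same wording in both sections.

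Two clarifications belong in the same edit:
- State whether the rule applies when onset is later than 1 hour, and that a run of a single time gives a duration of zero.
- In the sensitivity analysis of the primary variable, name the last retained time as the end of efficacy so defined.

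The cost is about one paragraph, and the final SAP version that Section 1 schedules before database lock is the natural place for it. The reported duration may be 1 to 2 hours shorter than Section 5 would have given.
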